10.7 Procedure(s) to account for missing or spurious data

Feasibility outcomes: For the feasibility outcomes relating to completeness of data there will be no need to account for missing data as this is exactly what the data is measuring fully completed or not (missing). Likewise, the number randomised will not need to account for missing data. For the proportion of sessions by patients in the PERFORM intervention arm, if the data for attendance at any session is truly missing and can be dissolved through data queries, individuals will be assumed to have not attend that session.

Patient outcomes/clinical events: sites will be asked to check completion of patient outcomes in order to mimimise any missing data. If items are missing from within an outcome questionnaire, the appropriate imputation method will be applied to allow outcome scoring. Data presentation for this feasibility study will consider completed outcomes and not impute any complete missing outcomes.

10.8 Other statistical considerations.

A statistical analysis plan will be finalised prior to final data lock and any deviations from the statistical plan will be reported in the statistical report.

[figure not shown]
Separate listings of SAEs will be presented as line listings; in addition to the description listing will include relatedness to intervention.

The number of serious adverse events will be presented overall and by randomised group. The number of patients with 0, 1, 2 etc events will be summarised overall and by randomised group.

The type and number (percentage) of protocol deviations will also be tabulated overall and by randomised group in the ITT population.

11. DATA MANAGEMENT

Data Flow Diagram

11.1 Data collection tools and source document identification

LCTU will be responsible for Data Management for the study and will undertake data validation, database queries/reviews in line with their SOPs.

ICH E6 section 1.51, defines source data as "All information in original records and certified copies of original records or clinical findings, observations, or other activities in a clinical trial necessary for the reconstruction and evaluation of the trial. Source data are contained in source documents (original records or certified copies)."

The basic concept of source data is that it permits not only reporting and analysis but also verification at various steps in the process for the purposes of confirmation, quality control, audit or inspection. A number of attributes are considered of universal importance to source data and the records that hold those data. These include that the data and records are:

- Accurate
- Legible
- Contemporaneous
- Original
- Attributable
- Complete
- Consistent
- Enduring
- Available when needed

Data collection tools and source document identification

Source Data is defined as the first place data is recorded, this will include:

- Medical Records
- Paper CRFs
- Participant reported outcome questionnaires

Data collection tools will comprise of:

- Macro Database (transcribed from CRFs) and direct source data entry
- Participant reported outcome questionnaires

The study researchers will seek consent from participants to re-contact them about taking part in future ethically approved research.

11.2 Data handling and record keeping

Records of study participant data will be made on study specific electronic CRFs. Trained member(s) of the site research team will enter data directly into a commercially available web based Clinical Data Management System (CDMS) provided by the LCTU (MACRO). On-entry validation checks will be applied where required and data entered will be checked for completeness, accuracy and timeliness by the site research team/trial manager/trial coordinator/data manager, with queries managed using the data clarification functionality within the CDMS system.

A copy of the patient feasibility study consent form and information sheet will be given to the participant, a copy will be placed in the hospital notes of all participants and original copies in the Investigator Site File. A sticker will be placed on the cover of the notes (or inside cover) detailing the study title, contact details of the PI and the fact that the notes should not be destroyed for 6 years from the end of the study. All study visits and related AEs/SAEs will be recorded in the hospital notes. Where electronic or hybrid medical notes are used it is expected that electronic flags, scanned documents and annotation are included in the medical notes.

For the post-intervention interviews consent forms completed virtually by the interviewer with the participant, the original, wet-signature consent form will be filed in an ISF at the Glasgow site, along with a copy of the consent transcription. A copy of the interviewer-signed consent form will be sent to the participant.

Participant and HCP interviews (as part of the interview schedule of this study) will be audio recorded. These recordings will be transcribed for analysis, and all identifying details removed. The audio and video recordings of the intervention sessions will be analysed by the research team and then destroyed once intervention fidelity is checked. All data collected will be stored in securely locked filing cabinets and in password-protected databases. After the project is complete, all data will be securely archived and will be destroyed after six years. Anonymised data will be stored in secure specialist data centre/repository relevant to this subject area and available for future research, should the participant consent to data storage.

During the study any paper CRFs and source data documentation will be stored in a secure area accessible to study site staff. Each enrolled participant will be allocated a unique study ID so that the CRFs and electronic database remains pseudonymised.

According to the ICH guidelines for Good Clinical Practice, the trial management team may check the CRF entries against the source documents, except for the pre-identified source data directly recorded in the CRF. LCTU will develop a monitoring plan for source data verification (SDV) checks. The informed consent form will include a statement by which the patient allows the Sponsor and LCTU's duly authorised personnel, the Ethics Committee, and the regulatory authorities to have direct access to original medical records which support the data on the CRFs (e.g., participant's medical file, appointment books, original laboratory records, etc.) in the event that this study is monitored by the study Sponsor. These personnel must maintain the confidentiality of all personal identity or personal medical information (according to confidentiality and personal data protection rules).

A Data Management Plan will be created with specific details on data handling and record keeping.

11.3 Access to Data

Direct access will be granted to authorised representatives from the Sponsor, LCTU, host institution and the regulatory authorities to permit study-related monitoring, audits and inspections- in line with participant consent.

Participants will also be given the opportunity to consent to the research team storing and sharing their anonymised data through secure specialist data centres/repositories relevant to the subject area for use in future research; this will optional and included on individual consent forms.

11.4 Archiving

Personal identifiable data generated by the study will be retained for six years following the notification of the end of the study before being destroyed in a confidential manner.

Following completion of the study data analysis, data and essential study records, including the final study report, will be archived in a secure location, for 6 years after the completion of the study. No study-related records, including hospital medical notes, will be destroyed unless or until the Sponsor gives authorisation to do so.

12. MONITORING, AUDIT & INSPECTION

The University of Leicester, as Sponsor, operates a risk-based monitoring and audit programme, to which this study will be subject. The LCTU operates a risk-based Quality Management System which will apply to this study with Quality Checks and Quality Assurance Audits performed as required.

The trial manager will undertake quality checks and assurance audits to ensure compliance with protocol, ICH GCP, and regulatory requirements.

All source data, study documents, and participant notes will be made available for monitoring, audits and inspections by the Sponsor (or their delegate), NHS Host Organisation, and the regulatory authorities, should a monitoring visit be undertaken.

13. ETHICAL AND REGULATORY CONSIDERATIONS

13.1 Research Ethics Committee (REC) review & reports

Once the initial sponsor review process is complete and a sponsor reference number has been allocated, and all requested documentation has been received and checked, authorisation from the University of Leicester's Research Governance Office will be issued to book further review of the proposed research. The NHS Research Ethics Committee and the Health Research Authority will then review the proposal. Agreement in principle is subject to the research receiving all relevant regulatory permissions. Submission for regulatory approvals will be submitted via Integrated Research Application System (IRAS). The Chief Investigator will ensure that all regulatory approvals, confirmation of capacity and capability from NHS sites and sponsor greenlight are in place before participants are approached.

For any required amendment to the study, the Chief Investigator, in agreement with the sponsor will submit information to the appropriate body in order for them to issue approval for the amendment. Amendments will be implemented upon receiving Sponsor Green Light.

The Research Governance Office's Standard operational procedures will be followed for the duration of the study.

Amendments will be submitted to the sponsor in the first instance for review and approval.

A trial master file will be maintained by the LCTU for the duration of the study and will be stored for six years after the study has ended. Each participating site will also maintain an investigator site file.

13.2 Peer review

This study has been peer reviewed by 2 independent experts working in or around the specialities of this study.

Peer review was also undertaken as part of the NIHR programme grant application process.

13.3 Public and Patient Involvement

Within the programme grant, PPI is constructed as a methodological activity and a Patient Advisory Group has been set up at Glasgow University, this group of patient and public representatives have contributed to the design of the research (including patient facing documentation) and will be involved in the management of the research and dissemination of findings.

13.4 Regulatory Compliance

Before the start of the study, approval will be sought from a REC for the study protocol, informed consent forms and other relevant documents. Any substantial amendments that require review by REC will not be implemented until the REC grants a favourable opinion for the study.

All correspondence with the REC will be retained in the Trial Master File and an annual progress report (APR) will be submitted to the REC by or on behalf of the CI within 30 days of the anniversary date on which the favourable opinion was given, and annually until the study is declared ended.

The Chief Investigator will notify the REC when the study has ended by completing the end of study notification form and will submit a final report of the results within one year after notifying REC.

13.5 Protocol compliance

If a protocol breach occurs, then the CI will document this in adherence to the University's Standard Operational Procedure SOP Identifying and Reporting Deviations and Serious Breaches of GCP and/or the Protocol for Trials. The CI will seek advice from the research supervisors and the sponsor.

13.6 Data protection and patient confidentiality

All information collected in the study will be kept strictly confidential.

The Chief Investigator will have access to the study documentation and will be the data custodian.

All investigators and research staff who have access to data will comply with the requirements of the General Data Protection Regulation (and other applicable regulations) with regards to the collection, storage, processing and disclosure of personal information and will uphold the Act's core principles.

Analysis of the feasibility trial data will be undertaken by the Chief Investigator on University of Leicester premises. All collected data and electronic confidential information will be saved on a secure drive at the University of Leicester.

PERFORM FEASIBILITY Protocol

Version 2.0 16.MAY.2023

Personal data of consenting participants (contact details) will be shared securely (using the University of Leicester secure file transfer service) with the University of Glasgow for the purposes of contacting participants regarding the qualitative interviews. It will be destroyed once the interviews have been completed. Other process evaluation data will be shared with the University of Glasgow and the University of Birmingham for analyses (fidelity data). Data transfer will be completed using the University of Leicester secure file transfer service. Any printed confidential material will be kept in a folder in a locked drawer in a secured room in a secure office environment office at the University of Glasgow or Birmingham.

A risk assessment through the University of Leicester will be completed for the sharing and transfer of pseudonymised data collected as part of this study with the listed collaborators for further analysis as part of the feasibility assessment of this study. This risk assessment will also include the transfer of patient information for the interviews being undertaken virtually through the University of Glasgow.

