6.8.3 Follow-up assessments

Follow up will be undertaken at 3-month follow up (3 months post randomisation).

 All measures identified above will be repeated. All outcome measures will be conducted by a blinded assessor who will have no knowledge of previous test results or treatment allocation.

6.8.4 4 and 6 month group maintenance sessions

Patients randomised to the PERFORM intervention exercise programme will be invited to attend 2 group maintenance sessions at 4 months post randomisation and 6 month post randomisation. These sessions will provide an opportunity provide additional support to participants, review long-term progress and address any further questions they may have.

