10.5 Interim analysis and criteria for the premature termination of the study

There are no formal criteria for stopping the study prematurely.

No interim analysis assessing the feasibility stop-go criteria with the possibility of early termination of the study is planned. However, due to the nature of the outcomes of recruitment and retention, these outcomes will be monitored along with serious adverse events throughout the study.

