13.10 Access to the final trial dataset

The Chief Investigator will have access to the full dataset.

Direct access will be granted to authorised representatives from the Sponsor and host institutions for monitoring and/or audit of the study to ensure compliance with regulations.

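### The Chief Investigator is named as analyst and the SAP need only precede data lock, while the adherence criterion still has open points that can move its colour; the exposure is modest

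*Protocol*

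**What the plan says.** **Who analyses.** Section 13.6: "Analysis of the feasibility trial data will be undertaken by the Chief Investigator on University of Leicester premises". The same section adds: "The Chief Investigator will have access to the study documentation and will be the data custodian". Section 13.10, on the final dataset, says: "The Chief Investigator will have access to the full dataset". The Leicester Clinical Trials Unit (LCTU) supplies randomisation (Section 6.6), and under Section 11.1 "LCTU will be responsible for Data Management for the study". No trial statistician is named as analyst. The only statistician mentioned is the independent member of the PSC.

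**When the SAP is fixed.** Section 10.8: "A statistical analysis plan will be finalised prior to final data lock". Deviations from it are to be reported. The protocol does not say who writes or approves it.

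**What is seen on the way.** Section 10.5 plans no interim analysis but says of recruitment and retention that "these outcomes will be monitored along with serious adverse events throughout the study". It does not mention adherence, and it does not say who does the monitoring.

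**What decides progression.** Section 2.2 sets Red, Amber and Green bands for recruitment, retention and adherence. Amber requires an action plan agreed with the PSC; Green goes straight to the main trial. The PSC agrees the criteria at the start and considers progression at the end.

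**The concern.** The primary outcome of this study is a classification of three counts against cut-offs. Such a result is sensitive to small decisions about definitions, because one rule can move a criterion across a boundary. Those decisions are best made before the counts are known, and the counts are best produced by someone who does not lead the programme under test. The protocol does neither explicitly: it assigns the analysis to the Chief Investigator and lets the SAP wait until just before lock.

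The Green boundary matters most, because the table in Section 2.2 writes in an action plan agreed with the PSC only for Amber. If adherence were called Green or not according to a reading chosen after attendance was known, the PSC would be working from a figure whose definition had not been fixed in advance.

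**Working it through.** No sample-size formula is involved. The check asks which of the three criteria the protocol leaves open, and whether the open points can change a colour.

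**1. The protocol's own figures.** Section 10.1 gives 60 patients, 40 and 20 by arm, with 20% loss at 3 months.
- 60 × 2/3 = 40 and 60 × 1/3 = 20, as stated.
- 60 × (1 − 0.20) = 48, and 48/60 = 80%, which is exactly the lower edge of Green for retention.

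**2. Bands as patient counts (Section 2.2).**

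| Criterion | Red | Amber | No colour | Green |
|---|---|---|---|---|
| Retention, of 60 | ≤38 | 39-47 | none | ≥48 |
| Adherence, of 40 | ≤15 | 16-19 | 20-23 | ≥24 |

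The adherence gap arises because Amber stops below 50% and Green starts at 60%: 20/40 = 50.0% and 23/40 = 57.5% fall in neither.

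**3. What is already fixed.**
- Recruitment is a count against 60 at 4.5 months (Section 2.3).
- Retention is complete EQ-5D at 3 months over all randomised (Sections 2.3 and 10.2.2), and Section 10.7 treats it as complete or missing.

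**4. What is open in adherence.**
- *Denominator.* Section 2.3 divides by 12 scheduled sessions. Section 7.1 describes six weeks at two sessions and two weeks at one: 6 × 2 + 2 × 1 = 14. Then 0.60 × 12 = 7.2, so at least 8 sessions; 0.60 × 14 = 8.4, so at least 9. A patient who attends exactly 8 is adherent on one reading and not on the other.
- *Uncoloured range.* With n = 40, the exact binomial probability of 20 to 23 adherent patients is 0.43 if true adherence is 50%, 0.47 at 55% and 0.36 at 60%. These rates are assumptions.
- *Missing attendance.* Section 10.7 counts a session as not attended if its record is missing and queries can resolve it. Read literally, that is the reverse of the evident intent, which is to cover records that queries cannot resolve.

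**5. Can the denominator change the category?** A beta-binomial simulation used 40 patients, 14 sessions and 20,000 trials per setting. Assumed mean attendance was 50% to 65%, with between-patient spread from wide to narrow (beta parameters summing to 1.5, 4 or 20). Moving the threshold from 8 to 9 sessions changed the category, counting the uncoloured range as one, in about 29% to 94% of simulated trials. It removed Green in about 2% to 70%. The protocol gives no attendance rates, so this shows only that the point can matter.

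**6. How often does one patient decide Green?** The relevant counts are 47 or 48 of 60 for retention and 23 or 24 of 40 for adherence. If the two are treated as independent, the chance that at least one criterion stands there is 1 − (1 − a)(1 − b).

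| True retention | True adherence | a | b | At least one |
|---|---|---|---|---|
| 80% | 60% | 0.246 | 0.248 | 43% |
| 70% | 50% | 0.070 | 0.138 | 20% |
| 70% | 70% | 0.070 | 0.083 | 15% |
| 90% | 75% | 0.013 | 0.022 | 3% |

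The top row puts both true rates exactly on the Green cut-off. Only the 80% retention figure comes from the protocol.

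**The case against.** **There is real oversight.** The PSC, with an independent chair and an independent statistician, agrees the criteria at the start and considers progression. LCTU manages the data and plans source data verification. This stands. A reader might infer that the Chief Investigator alone settles go or no-go, and the documents do not support that.

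**Pre-lock SAP finalisation is ordinary practice.** This also stands. The protocol does not say that the Chief Investigator writes or approves the SAP, and the SAP is not shown. But Section 13.6 positively names the analyst, so a SAP that named someone else would contradict it.

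**Early sight of data is not shown.** Section 13.10 concerns the final dataset, and Section 11.2 gives data entry and checking to site and trial staff. It is fair to say that the protocol neither grants nor rules out a view of accruing attendance by the Chief Investigator.

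**Blinding is beside the point.** A reader might object that the analyst is unblinded, since the only blinding stated is at follow-up: "All outcome measures will be conducted by a blinded assessor who will have no knowledge of previous test results or treatment allocation". For the progression criteria this hardly matters. Recruitment and retention are pooled over arms and adherence is measured in one arm, so withholding by-arm summaries would protect none of the three.

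**Retention and missing attendance are not loose.** Mostly true. Counting an unresolved session as not attended works against Green. The rule needs its wording repaired, not a new principle.

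**The single-patient probability is a worst case.** Correct for the 43%. Patients who drop out would also plausibly fail both criteria, so independence is doubtful. Being one patient from a cut-off is also not the same as having a disputable record there.

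**Conclusion.** The point holds in a limited form and is minor. The protocol names as analyst the person who leads the programme, and it allows the SAP to be finalised as late as data lock while recruitment and retention are being watched. The colour can still be moved mainly through adherence: the 12 against 14 session conflict, the uncoloured 20 to 23 of 40, and the garbled missing-attendance rule.

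The size depends on true rates that the protocol does not give. The uncoloured range would be hit with probability 36% to 47% if true adherence is 50% to 60%. A single patient would decide Green on retention or adherence with probability of about 3% to 43% over the rates tried, under independence. The 43% should not be quoted alone.

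That the Chief Investigator has an interest in the answer is an inference from the role. Nothing in the documents suggests improper conduct.

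**What to change.** **Section 13.6.** Replace the sentence on analysis with wording such as: *The analysis will be carried out from the locked database, according to the SAP, by a statistician independent of the Chief Investigator (for example at the LCTU). The report will go to the PSC at the same time as to the Chief Investigator.*

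**Section 10.8.** Require the definitions of the three co-primary outcomes to be agreed with the PSC and signed off before attendance or 3-month data are reviewed. The rest of the SAP may still follow before data lock.

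**Before that sign-off**, reconcile the adherence passages:
- the session count in Section 2.3 with the schedule in Section 7.1;
- the bands in Section 2.2, so that every percentage has a colour;
- the missing-attendance sentence in Section 10.7.

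Which session count is right, and which colour the gap should take, is for the sponsor and the PSC to settle.

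**Cost.** A few sentences, and those definitions must be finished some months earlier. LCTU and the PSC's independent statistician already have roles in the study.
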